1.0 PROTOCOL SUMMARY AND SCHEMA

[figure not shown]
Breast implant failure (defined as removal or replacement with another reconstruction) and capsular contracture are longstanding adverse effects of postmastectomy radiation (PMRT) in patients who have undergone immediate expander/implant reconstruction. These complications can impact cosmesis and quality of life. A prior departmental protocol, IRB #10-025, demonstrated the feasibility and safety of multi-beam IMRT in treating locally advanced breast cancer patients requiring comprehensive PMRT. By permitting the delivery of a more homogeneous radiation dose and fewer and smaller —hot spots— to the implant compared to conventional RT techniques, we hypothesize that multi-beam IMRT can minimize implant-related side effects of RT, leading to improved implant-specific outcomes and cosmesis in breast cancer patients with implant reconstruction undergoing PMRT. Efficacy is the primary endpoint of this study and is defined as relative 30% decrease in implant failure rates following the completion of IMRT. Secondary endpoints are to assess cosmesis, quantify minor revisional surgery rates and to evaluate the correlation between MRI changes in the implant and the degree of capsular contracture as ascertained by standard assessment methods. There are several exploratory endpoints in a subset of the study population: 1) to assess the feasibility of performing a cardiac PET scan in the IMRT treatment position in order to quantify the cardiac dose delivered to the heart 2) to assess early subclinical cardiotoxicity associated with IMRT, utilizing speckle tracking strain echocardiography, ultrasound of the brachial artery, cardiopulmonary exercise testing (CPET), fatigue and quality of life questionnaires and cardiac biomarkers 3) to assess the effect of IMRT on quality of life and fatigue.

The time interval at which follow-up assessments will occur after the intervention (IMRT) will depend on the sequencing of the expander/implant exchange with radiation. Two groups of patients will be evaluated. Group 1 will consist of patients who receive IMRT to the permanent implant and are followed up at 12 ± 2 months and 24 ± 2 months after IMRT. Group 2 will include patients who receive IMRT to the temporary expander and are followed up at $12-18 \pm 2$ months and 30 ± 2 months after IMRT. This sequencing will be determined prior to study enrollment based on whether the patient received neoadjuvant or adjuvant chemotherapy (see Section 3.0 for further details).

Evaluation for implant failure may occur at any time interval between the completion of IMRT to the end of the study period (24 ± 2 months for Group 1 or 30 ± 2 months for Group 2, after IMRT). Capsular contracture and cosmesis will be assessed at baseline, 12 ± 2 months and 24 ± 2 months for Group 1 or $12-18 \pm 2$ months and 30 ± 2 months for Group 2, both following IMRT. The patient will be evaluated for capsular contracture by physical exam and an optional breast MRI, and for cosmesis by Breast-Q[®] questionnaires at these time points. A subset of 10 patients evaluated with cardiac PET scans for exploratory objective #1 will obtain these studies at the time of the RT simulation session and $12-18$ months (± 6 months) after the completion of IMRT. A separate subset of 20 patients to be evaluated for exploratory objectives #2 and #3 will complete the study questionnaires and undergo speckle tracking strain echocardiography, ultrasound of the brachial artery, CPET, and cardiac biomarker measurement at baseline and at the post-treatment intervals specified in Section 10.

Target accrual for this study is 130 patients, to be achieved in 3-4 years of accrual.

Schema

¹**Group 1:** Physical examination by MD, optional Breast MRI, Breast-Q[®] at baseline (after permanent implant exchange, physical exam and Breast-Q[®] may be done after the initiation of IMRT), 12 ± 2 months and 24 ± 2 months post-IMRT. Total length of the follow-up time will be 24 ± 2 months post-IMRT.

²**Group 2:** Physical examination by MD, optional Breast MRI, Breast-Q[®] at baseline (after permanent implant exchange and after IMRT), 18 ± 2 months and 30 ± 2 months post-IMRT, as these patients will undergo exchange of the temporary expander for the permanent implant approximately 4-8 months following the completion of radiation (at the discretion of the treating plastic surgeon). Total length of the follow-up time will be 30 ± 2 months post-IMRT.

2.0 OBJECTIVES AND SCIENTIFIC AIMS

2.1 Primary Objective

To evaluate the efficacy of multi-beam IMRT in decreasing the rate of implant failure in breast cancer patients who have undergone two-stage expander/implant reconstruction and require PMRT. Implant failure is defined as a surgery requiring removal or replacement of the prosthesis with another type of reconstruction.

2.2 Secondary Objectives

- To quantify the incidence of moderate to severe capsular contracture
- To quantify the rates of minor revisional surgeries
- To evaluate cosmesis
- To quantify post-radiation volumetric and capsular changes on MRI and correlate these changes with clinical assessments of capsular contracture.

2.3 Exploratory Objectives

- To evaluate the feasibility of performing $^{13}\text{N}-\text{NH}_3$ PET/CT scans within the radiation simulation session and correlate CFR and IMRT dose to the heart.
- To evaluate the effect of IMRT on early subclinical cardiotoxicity, as measured by speckle tracking strain echocardiography, ultrasound of the brachial artery, CPET, fatigue/quality of life questionnaires and cardiac biomarkers.
- To evaluate the effect of IMRT on fatigue and quality of life, as measured by FACT-B and FACIT questionnaires.

3.0 BACKGROUND AND RATIONALE

Enhancement of survival and preservation of quality of life represent two paramount goals in the treatment of breast cancer. The results of a large meta-analysis established the critical role of PMRT therapy plays in improving disease-free survival in locally advanced breast cancer patients [1]. At the same time, breast reconstruction offers psychosocial and cosmetic benefits to patients who undergo mastectomy and is considered an important component of treatment [2]. In spite of the individual merits of PMRT and reconstruction, the optimal integration of the two modalities has been controversial. Radiation is an independent risk factor for complications in patients with implant reconstructions, including a 2-3-fold increase in the risk of significant capsular contracture (Baker grade III or IV), increased rates of reconstructive failure (3-5 fold increase), decreased satisfaction, and decreased cosmetic outcomes [3,4].

Capsular contracture, in particular, is problematic in patients with implant reconstructions who have received radiation, often leading to pain, discomfort and reconstructive failure. After reconstructive surgery which involves the positioning of an implant under the chest wall, capsules of tightly woven collagen fibers commonly form around the implant [5]. In some patients, the interaction between inflammatory cells, extracellular matrix, and fibroblasts leads to an abnormal response, causing thickening and tightness of the capsule and hence, capsular contracture [6,7]. Factors such as radiation, subclinical infections, hematoma or the absence antibiotics during surgery have been proposed as etiologies of capsular contracture, but the contributions of each of these factors to the

development of capsular contracture is unknown [8-10]. Several studies of pharmacologic intervention for capsular contracture have been published, but lacked the evidence to be used as a true therapeutic measure [11,12]. When severe, capsular contracture can compromise the aesthetic outcome and require surgical intervention such as an open capsulotomy, capsulectomy or removal or replacement of the implant.

MSKCC's institutional experience of 151 patients who received PMRT following expander/implant reconstruction, the 7-year permanent implant failure rate was 29%, with the majority of events occurring within 1-2 years after radiation. Infection was a major cause of implant removal, whereas capsular contracture was the most dominant cause for implant replacement. This data is consistent with multiple reports in the literature where capsular contracture remains the most significant long-term risk following irradiation of implant reconstructions, even with improvements in implant technology and surgical techniques over the past decade [13-16]. Recently, additional data from MSKCC has been published by Cordeiro et al [51], which demonstrated that implant failure rate was higher when patients were irradiated to the tissue expander vs. the permanent implant, thereby demonstrating the significance of the timing of radiation therapy relative to reconstruction when assessing reconstructive outcomes.

Existing Methods for Assessing Capsular Contracture and Cosmesis After Implant Reconstruction

To date, the standard tool for estimating the presence and severity of capsular contracture is the Baker scale, which was developed in 1979 and consists of a standardized 4-point scale that integrates the appearance, texture and tenderness of the examined breast. Studies have shown that the Baker score can be subjective and lead to inter-rater (and possible intra-rater) variability [5].

Methods such as measurement of pressures inside the breast pocket using tonometry or other techniques have been attempted. However, none of these tools have gained widespread acceptance. Subsequently, there is difficulty in assessing the extent of capsular contracture, resulting in a wide range of capsular contracture rates reported in the literature [17]. The lack of an objective way to measure capsular contracture has hindered efforts to establish standardized treatment guidelines for capsular contracture.

The use of radiologic tests to quantify capsular contracture appear promising. To date, the only study in which capsular thickness on imaging tests have been correlated with the Baker scoring system is a cross-sectional study of 22 patients who underwent breast reconstruction with implants and followed by clinical assessment of the capsular contractures with MRI to evaluate the radiologic thickness of the capsule. Not all patients received radiation. MRI revealed the distinct appearance of the thickened capsule and correlated well with the Baker scoring system. Parameters measured on MRI included capsular anterior-posterior diameter, left-right diameter and capsular thickness. A statistically proven correlation was found between capsular thickness on MRI and the clinical Baker score (p-values =0.02). A Baker score of I or II correlated with a thinner capsule averaging 1.14 mm, whereas a Baker score of III or IV correlated with a thicker capsule averaging 2.62 mm [18].

[figure not shown]

Figure 1. Image C denotes a normal breast capsule on MRI. Image D shows a thickened capsule correlating with capsular contracture. Images adapted from Zahavi et al [18].

Objective assessment of overall cosmesis is also important when comparing aesthetic outcomes in implant reconstruction. The majority of studies assessing cosmesis have relied on photographic analysis by healthcare providers to analyze various measures including symmetry, scars, volume or shape, or they have used non-validated questionnaires which make their findings somewhat less useful. These tools do not address patient perceptions and can either over or underestimate the success rates of various reconstructive surgeries from a cosmetic point of view. Recently, a validated patient reported outcome tool, the Breast-Q[®] which was developed by investigators at MSKCC[19], has addressed this deficiency. The Breast-Q[®] will analyze how patients perceive their reconstruction and help guide analysis of outcomes that can then be standardized across centers. A detailed description of the Breast-Q[®] is provided in section 9.3.2.

Sequencing of Radiation with Expander/Implant Reconstruction

We have published that exchanging the expander to the implant prior to the start of radiation therapy is associated with excellent long-term clinical outcomes and acceptable complication rates in patients who received adjuvant chemotherapy [20]. Thus, in these patients (represented in Group 1), our institutional policy is to initiate radiation after the expander has been exchanged for the permanent implant.

In approximately 30-40% of locally advanced breast cancer cases, upfront surgical down-staging of the tumor with systemic therapy is required and therefore these patients received neoadjuvant chemotherapy, followed by mastectomy with immediate tissue expander placement (represented in Group 2). In such patients, there is often inadequate time to complete expansion, perform exchange and achieve adequate tissue healing prior to initiating radiation. Hence, the exchange procedure for a permanent implant is delayed until approximately 4-8 months after the end of radiation, when the tissues have recovered from radiation injury as determined by the treating plastic surgeon. Radiation is subsequently delivered to the tissue expander and regional lymph nodes.

Over the past several years, over 50% of locally advanced breast cancer patients who receive postmastectomy radiation therapy at MSKCC are treated with comprehensive radiation therapy to the chest wall and regional lymph nodes [departmental statistics]. Regional lymph node irradiation includes the axillary, supraclavicular and internal mammary nodes. PMRT therapy has been shown to positively impact disease free survival and overall survival [21-24]. The most recent meta-analysis from the Early Breast Cancer Trialists' Collaborative Group (EBCTCG) showed that adjuvant radiation therapy improved 15-year breast cancer mortality in node positive patients treated with mastectomy and lymph node dissection[1]. Twenty-four of the 25 PMRT studies included in the EBCTCG meta-analysis performed Internal Mammary Node (IMN) irradiation, suggesting that the benefits of PMRT may be

related to their treatment [1]. Interest in IMN irradiation has recently been fueled by the results from the National Cancer Institute of Canada (NCIC) MA-20 trial demonstrating improved distant disease-free survival and a favorable trend in overall survival in breast-conservation patients receiving comprehensive regional node treatment[25].

Despite its clinical benefits, routine irradiation of the IMNs in PMRT remains controversial because of the increased cardiac and pulmonary toxicity that results from targeting the internal mammary nodes, which lie in the first three intercostal spaces in the parasternal region, directly above the heart. Conventional 3D-conformal RT refers to a treatment technique where two tangential beams deliver dose to the chest wall while an anterior oblique beam is used to treat the axillary nodes. It has been shown that when conventional radiation techniques are utilized, the presence of an implant reconstruction can further increase heart and lung doses in patients requiring PMRT, compared to patients who do not have reconstructions[26,27]. The presence of an implant or temporary expander often poses technical challenges in delivering a homogeneous dose to the chest wall secondary to the sharp slope of the implant on the chest wall, compared to a flat chest wall (**Figure 2**).

[figure not shown]

Figure 2. The left panel demonstrates an unreconstructed chest wall. The electrons (orange) targeting the IMNs are junctioned with a —clean match— against the photon tangent beams (red). In contrast, in a patient with an implant reconstruction (right panel), the sharp slope of the implant creates an imperfect match between the electrons and photons, creating a —cold— triangle (blue arrow) region of dose heterogeneity.

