9.3 Assessment of Secondary Objectives

9.3.1 Capsular Contracture

Two methods will be employed to assess capsular contracture. These include the current standard assessment tool, the Modified Baker score, and MRI. All follow-up assessments will be compared to the baseline assessments. For all patients, the radiation oncologist should perform the baseline physical evaluation 3-10 weeks after the patient's exchange surgery.

Baker Scoring System (See Appendix 1)

All patients will be assigned a Baker Classification score at baseline and at each follow-up interval by the radiation oncologist and plastic surgeon. The Baker score is a standardized 4-point scale, which integrates the texture and appearance of the breast. Grade I is a normal-appearing, soft breast (a Grade IA breast cannot be detected as an implant, while the implant of a Grade IB breast can be detected by physical examination or inspection); Grade II refers to breast implants that are firm but

appear normal; Grade III includes implants that are firm and appear abnormal; Grade IV capsular contracture is the most severe and includes breasts that are hard, painful, and appear abnormal often with severe distortion [46].

Breast MRI

Longitudinal MR studies will be evaluated for capsular contracture.

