14.1.2 Capsular Contracture

For the secondary objectives, the incidence of moderate and severe capsular contracture will be examined using proportions of patients who developed Baker grade <II and \geq II capsular contracture, respectively, at 12 or 18 months and 24 or 30 months after IMRT was administered. Incidence of minor revisional surgeries by plastic surgeon will be evaluated by proportions too. Again, the rates (proportions) will be compared across the two groups.

To evaluate cosmesis, the Breast-Q[®] will be utilized in these assessments and will be presented descriptively, giving summary statistics for changes in the Breast-Q[®] scores over time.

Post-treatment MRI outcome is defined as a continuous variable. We will examine the correlation between the 12-month MRI and 12-month Baker score (<II vs \geq II in Group 1 and between the 18-month MRI and 18-month Baker's score in Group 2. The correlation will be assessed by Wilcoxon rank sum tests. We will also examine the sensitivity and specificity of MRI by using Baker score as the gold standard. All patients enrolled will be used for the analysis of secondary objectives if they provided eligible measurements. Analyses for secondary objectives will be done separately for the two groups.

14.1.3 $^{13}\text{N-NH}_3$ PET/CT Feasibility Endpoint

We will assess the feasibility of performing $^{13}\text{N-NH}_3$ PET studies in breast cancer patients undergoing IMRT within the RT simulation session. This involves delivering the dose on time (taking into account the short half life of $^{13}\text{N-NH}_3$), performing all scans successfully, and most importantly, having the patient tolerate all imaging sessions while in the treatment position.

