16.1 Data Collection

The following data forms (found in the regulatory binder) and appendices (found on ProtocolWeb) will be completed and entered into CRDB at specified time points according to the tables below:

Groups 1, 2, 2A:

Time Points:	Data Forms / Appendices:	To Be Completed By:
Baseline (Pre-Treatment)	• Minimal Data Set in CRDB (within 2 weeks of registration)	RSA
	• Data form 1: Patient Information	RSA
	• Appendix 3: Dose Parameters	Dosimetrist
3-10 Weeks Post-Exchange Surgery AND Follow-up	• Appendix 4a or 4b: Breast-Q Questionnaire	Patient
	• Dataform 3a: Evaluation of Capsular Contracture & Cosmesis by Radiation Oncologist	Radiation Oncologist
	• Dataform 3b: Evaluation of Capsular Contracture & Cosmesis by Plastic Surgeon	Plastic Surgeon
	• Data form 4: MRI Assessment	Radiologist

Groups 2A & 2B:

Time Points:	Data Forms / Appendices:	To Be Completed By:
Baseline: 0-4 Weeks Pre-RT (Group 2A) OR 4-8 Weeks Post-Mastectomy (Group 2B)	• Appendix 10: CPET Form	Exercise Physiologist
	• Appendix 11: CPET Recording Sheet	Exercise Physiologist
Follow-up: 2-4 Weeks Post-RT (Group 2A) OR 15-20 Weeks Post-Mastectomy (Group 2B)	• Appendix 12: FMD Form	Exercise Physiologist
	• FACIT and FACT-B Questionnaires	Patient

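### Two clinicians assign a Baker grade at each assessment point, but Section 14.1.2 analyses one unspecified Baker score and plans no use of the paired ratings

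*Combined protocol and SAP*

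**What the plan says.** Section 3.0 says of the scale: "Studies have shown that the Baker score can be subjective and lead to inter-rater (and possible intra-rater) variability".

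Section 9.3.1 requires two raters: "All patients will be assigned a Baker Classification score at baseline and at each follow-up interval by the radiation oncologist and plastic surgeon". Section 16.1 lists a form for each, completed by that specialist: "Dataform 3a: Evaluation of Capsular Contracture & Cosmesis by Radiation Oncologist" and "Dataform 3b: Evaluation of Capsular Contracture & Cosmesis by Plastic Surgeon". No consensus form is listed.

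Section 14.1.2 then has three Baker-based analyses.

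- Contracture incidence is to be "examined using proportions of patients who developed Baker grade" below II, or II and above.
- For the MRI association: "We will examine the correlation between the 12-month MRI and 12-month Baker score", with the 18-month equivalent in Group 2. The test is a Wilcoxon rank sum test of continuous MRI across the two grade categories.
- For diagnostic accuracy: "We will also examine the sensitivity and specificity of MRI by using Baker score as the gold standard".

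The analysis set is broad: "All patients enrolled will be used for the analysis of secondary objectives if they provided eligible measurements". The secondary analyses are run separately in the two groups.

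Footnote c to the Group 1 and Group 2 schedules in Section 10 lets the plastic surgeon's follow-up be timed either from the end of radiation or from exchange surgery.

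**The concern.** Each of the three analyses needs one classification per patient per time point, and the data will hold two. The plan does not say whether to use the radiation oncologist's grade, the surgeon's, a consensus or an average. If this is settled after the data are seen, the first-listed secondary objective and the reference standard for MRI both rest on an unplanned choice.

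There is also a missed opportunity. The background section says the scale varies between raters and ties the difficulty of assessing contracture to the wide range of published rates. The trial collects the paired ratings needed to measure that variability and reduce its effect, but 14.1.2 gives them no role.

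Timing adds to this. In Group 2 the two grades for one nominal visit can be months apart, so the choice of rater can also decide which state of the breast is compared with the MRI.

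**Working it through.** **No plan figure to reproduce.** The documents give no sample size, power, agreement or incidence figure for the Baker analyses. Sections 3.0, 9.3.1, 10, 12, 14.1.2 and 16.1 contain no rater rule, combination rule or agreement analysis. Everything below that is not a date or a count is an assumption.

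**1. Incidence, one rating against the average of two.** Suppose each examiner grades a proportion p positive, with agreement kappa k. The variance of one examiner's proportion is p(1−p)/n. The variance of the average of the two is p(1−p)(1+k)/(2n). The ratio is (1+k)/2:

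- k = 0.4: 0.70, a 30% reduction in variance
- k = 0.6: 0.80, a 20% reduction

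**2. Incidence under a combination rule.** P(both) = p² + k·p(1−p), and P(either) = 2p − P(both). At p = 0.30:

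| kappa | both positive | either positive |
|---|---|---|
| 0.4 | 0.09 + 0.084 = 17.4% | 60 − 17.4 = 42.6% |
| 0.6 | 0.09 + 0.126 = 21.6% | 38.4% |
| 0.8 | 0.09 + 0.168 = 25.8% | 34.2% |

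These rows show what a combination rule can do. They do not show the effect of choosing one examiner over the other, which here gives 30% either way. That choice shifts incidence by exactly the difference between the examiners' own rates.

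**3. MRI association.** Assume single-rating reliability 0.5, meaning half the variance is true and half is error.

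- Independent errors: reliability of the mean is 0.5/(0.5 + 0.25) = 0.667, so the correlation with MRI rises by √(0.667/0.5) = 1.155.
- Errors correlated at 0.5: error variance of the mean is 0.5 × (1 + 0.5)/2 = 0.375, reliability is 0.5/0.875 = 0.571, and the factor is √(0.571/0.5) = 1.07.

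Simulated power at n=40 and true r=0.6, with four-level grades:

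| Analysis | One rater | Mean of two, errors correlated 0.5 | Mean of two, independent errors |
|---|---|---|---|
| Wilcoxon, cut at II (planned test) | 0.53 | 0.61 | 0.67 |
| Spearman, ordinal grade | about 0.68 | 0.77 | 0.83 |

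A rerun with an assumed grade mix of 40/30/20/10% gave closely similar values. The Wilcoxon gain depends on counting a I/II pair (mean 1.5) as below II. Counted as II or above, the gain largely disappears, which is a reason to keep the mean grade ordinal. For scale, one third of 130 is about 43 patients in Group 1, and MRI is optional.

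**4. MRI accuracy against a fallible reference.** Assume prevalence 0.30, true MRI sensitivity and specificity 0.90/0.90, and independent errors.

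- Against an examiner who is 0.90/0.90: apparent sensitivity is (0.3×0.9×0.9 + 0.7×0.1×0.1)/(0.27 + 0.07) = 0.250/0.34 = 73.5%. Apparent specificity is (0.567 + 0.003)/0.66 = 86.4%.
- Against an examiner who is 0.90/0.80: sensitivity is 0.257/0.41 = 62.7% and specificity is 0.507/0.59 = 85.9%.

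The same scans can therefore look different against two examiners who differ only in specificity.

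**5. Timing.** Group 2 exchange is about 4-8 months after radiation (Section 10, Group 2 schedule). A surgeon's 18-month visit counted from exchange falls 18 + 4 = 22 to 18 + 8 = 26 months after IMRT. That is nominally 4-8 months later than the radiation oncologist's 18-month grade.

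**The case against.** The strongest reply is that 14.1.2 is merely silent. A reader might infer that half the ratings are wasted or discarded, but the text does not say so. A consensus or combined grade is not excluded, and the forms themselves sit in a regulatory binder outside these documents. This stands: what can be said is that no use of the paired ratings is specified.

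A reader might also infer that incidence could run from about 17% to 43% depending on whose grade is used. The documents do not support that. The spread comes from both-positive and either-positive rules that no section proposes, at an assumed rate and kappa. With equal examiner rates, swapping one for the other changes nothing.

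Nor may the Spearman power be read as the plan's own, since the planned test is a two-category Wilcoxon. Its power is lower and its gain from the second rating more modest.

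Averaging has a weakness too. Both raters are treating clinicians, their errors may be correlated, and their grades may be taken months apart, so a naive mean could match neither date to the MRI. This also stands. It is why the gain is given as a range and why the fix needs a timing rule.

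Finally, these are secondary analyses without a decision rule in a single-arm phase II trial, and Section 12 calls the MRI quantification descriptive. That limits the importance of the point. It does not supply the missing rule, and both ratings are already required.

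**Conclusion.** The point holds in limited form. Two separately recorded Baker grades are required at each assessment point. Section 14.1.2 analyses one unspecified score for incidence, the MRI association and MRI accuracy, and nothing in the documents says how the pair is to be used or its agreement measured. The primary endpoint and Breast-Q are untouched.

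The case for change is that a better method is nearly free. Under the stated assumptions, averaging cuts the variance of the incidence estimate by 20-30%. It adds about 0.08-0.14 to the power of the planned MRI test, and about 0.09-0.15 to that of a Spearman analysis. These sizes rest on assumed kappa, reliability, correlation and sample size. They illustrate the gain and do not predict it for this trial.

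**What to change.** Amend Section 14.1.2 as follows.

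1. Report contracture incidence for each examiner. Name the average of the two proportions as the prespecified summary, with a patient-clustered confidence interval.
2. Report weighted kappa between the examiners at each assessment point.
3. For the MRI association, use the mean of the two grades, kept ordinal (for example Spearman). Keep the planned Wilcoxon test at the II cut, run for each examiner, as a supporting analysis.
4. Report MRI sensitivity and specificity against each examiner separately.
5. Pair or average only grades taken within the same post-IMRT window as the MRI, because the surgeon's visit may be timed from exchange surgery.

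The cost is a few lines of text and a little more analysis. Some pairs will be lost to timing mismatch, mainly in Group 2. No assessor, visit or form is added.
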